1.1.4.6. Relapsed and/or Refractory Multiple Myeloma

The early development of ixazomib in patients with RRMM involves 2 studies (C16003 and C16004) with similar objectives, but each investigated 1 of the 2 dosing schedules commonly used with the first-in-class proteasome inhibitor, VELCADE. Study C16003 is an open-label, dose escalation, phase 1 study of ixazomib dosing on a twice-weekly schedule on Days 1, 4, 8, and 11 of a 21-day cycle in adult patients with RRMM. (25) Study C16004 is an open-label, dose escalation, phase 1 study of ixazomib dosing on a weekly schedule on Days 1, 8, and 15 of a 28-day cycle in adults patients with RRMM (26, 27). Both studies have now completed enrollment. The DLTs in Study C16003 were rash macular and thrombocytopenia and the DLTs in C16004 were nausea, diarrhea, vomiting, and erythema multiforme.

In the dose escalation component of both studies, patients had multiple myeloma that had relapsed following at least 2 lines of therapy that must have included bortezomib, thalidomide (or lenalidomide), and corticosteroids. In both studies, when the MTD was established, cohorts of patients representing the heterogeneous patient population currently seen in clinical practice were to be enrolled into 1 of 4 expansion cohorts, including a relapsed and refractory cohort, a carfilzomib cohort, a proteasome inhibitor-naïve cohort, and a VELCADE-relapsed cohort.

Final study results are currently being analyzed, but preliminary data suggest that ixazomib has anti-tumor activity in heavily pretreated MM patients, with durable responses/disease control, and is generally well tolerated. Please refer to the **ixazomib IB and SMA** for further information.

1.1.4.7. Newly Diagnosed Multiple Myeloma (NDMM)

Multiple research paths are being explored in patients with NDMM with a focus on evaluating ixazomib in combination with agents commonly used across treatment settings. The development of ixazomib in combination with lenalidomide with dexamethasone (LenDex) in patients with NDMM who are transplant eligible or ineligible involves 2 studies (C16005 and C16008) with similar study designs except for a few key differences, namely the schedules of ixazomib and dexamethasone . Ixazomib is also being evaluated in combination with melphalan and prednisone (MP) for patients who are not transplant eligible due to age or coexisting morbidity (in Study C16006).

All 3 studies are phase 1/2, with phase 1 focusing on safety and phase 2 on efficacy (and further characterization of safety). Please refer to the ixazomib IB and SMA for further information.

1.1.4.8. Clinical Trial Experience Using IV Ixazomib

See the **IB** for descriptions of the 2 studies that investigated IV ixazomib in advanced solid tumors and advanced lymphoma (Studies C16001 and C16002, respectively).

1.1.4.9. Preclinical Activity of Oral Ixazomib in Myeloma Bone Disease

Ixazomib has demonstrated both preclinical and clinical activity. Gomez et al investigated its bone anabolic and antiresporptive effects in myeloma and in comparison with Bortezomib (VELCADE) in preclinical models. Clinically achievable concentrations of Ixazomib markedly inhibited osteoclast formation and resorption in ex vivo experiments, as well as promoted osteoblast differentiation and function (even in osteoprogenitor cells from MM patients with osteolytic lesions). In a mouse model, Ixazomib was found to be at least as effective as intraperitoneally administered Bortezomib in the control of myeloma growth and in the prevention of bone loss (28).

1.2. Study Rationale

Bortezomib has been shown to produce on anabolic bone effect in relapsed/refractory MM patients . The next generation proteasome inhibitor, Ixazomib, has been evaluated in a pre-clinical setting and has demonstrated to be as equally effective to Bortezomib in both controlling tumor burden and providing a significant benefit in associated bone disease (as sustained by both bone anabolic and anticatabolic activities (28).

Consequently, it is conceivable that this agent may achieve bone beneficial effects in addition to its anti-myeloma activity in multiple myeloma patients. Therefore, this study is designed to focus on the bone anabolic effect of Ixazomib (MLN 9708) on MM patients, with the primary objective of determining the effect of a short course of ixazomib (6 cycles) on changes in bone on formation markers (BALP,

osteocalcin) and bone densitometry (Dexascan) indicies. The dose of ixazomib will be given as 4mg weekly in a 28 day cycle for a maximum of 6 cycles.

1.3. Potential Risks and Benefits

Please refer to the current ixazomib Investigator's Brochure (IB) and Safety Management Attachment (SMA).

Risks of study drug:

Blood and lymphatic system disorders: Lymphopenia. Reductions in blood counts may predispose patients to an increased susceptibility to infection (see Infections and infestations below). A rare risk is thrombotic thrombocytopenic purpura, a rare blood disorder where blood clots form in small blood vessels throughout the body, characterized by thrombocytopenia, petechiae, fever, and possibly more serious signs and symptoms. Reticulocytopenia was described in animals and may be associated with anemia. These potential risks should be managed according to standard medical practice.

Gastrointestinal disorders: Intestinal obstruction including ileus and intussusception (described in animal studies), abdominal pain.

General disorders and administration site conditions: Chills, influenza like illness.

Infections and infestations: Pneumonia. Lymphopenia may be associated with increased risk of infection, including re-activation of herpes zoster. Antiviral therapy may be initiated as clinically indicated.

Investigations: Blood creatinine increased (see Renal and urinary disorders below).

Metabolism and nutrition disorders: Dehydration, electrolyte imbalance.

Musculoskeletal and connective tissue disorders: Back pain, myalgia, arthralgia, bone pain, pain in extremity.

Nervous system disorders: Headache, syncope. In addition, autonomic and motor neuropathy may be observed, as both have been reported for VELCADE, another proteasome inhibitor. Posterior reversible encephalopathy syndrome (PRES) has been reported with ixazomib. PRES has also been reported for VELCADE (refer to VELCADE for Injection Package Insert) and Kyprolis.(10) Transverse myelitis has also been reported with ixazomib. It is not known if ixazomib causes transverse myelitis; however, because it happened to a patient receiving ixazomib , the possibility that ixazomib may have contributed to transverse myelitis cannot be excluded.

Renal and urinary disorders: Renal impairment, renal failures, and renal failure acute have been reported in association with dehydration due to nausea, vomiting, anorexia, and/or diarrhea, the use of nonsteroidal anti-inflammatory drugs (NSAIDs), and/or disease progression. In one situation, this has been severe, requiring temporary dialysis.

Respiratory, thoracic and mediastinal disorders: Dyspnoea, cough, upper respiratory tract infection, pneumonitis.

Skin and subcutaneous tissue disorders: A rare risk is Stevens-Johnson syndrome, a severe, lifethreatening or deadly rash with skin peeling and mouth sores, which should be managed symptomatically according to standard medical practice. Stevens-Johnson syndrome has also been reported for VELCADE (refer to VELCADE for Injection Package Insert(10)). It is also reported as risk with lenalidomide, an agent used in the treatment of hematologic malignancies including in combination with proteasome inhibitors. For more information about this risk with lenalidomide, refer to the Revlimid (lenalidomide) Package Insert.(11)

Vascular disorders: Hypotension, orthostatic hypotension.

Other: Acute phase response that may result in fever and metabolic changes (observed only in

nonclinical studies). Infrequent incidences of tumor lysis syndrome have also been reported.

Potential Benefits:

The clinical benefit of ixazomib continues to be studied in a comprehensive and global development plan that involves studies sponsored by Millennium. Ixazomib appears to show early signs of antitumor activity as evidenced by at least 50% reduction in disease burden in some patients, including patients that have been heavily pretreated as well as those with newly diagnosed MM, and prolongs stabilization of the underlying disease in other patients across all ongoing trials. The preliminary findings are favorable when considering historical and currently available therapies for the patient populations evaluated. Though additional data are needed to characterize the clinical benefit of this drug, the emerging data supports expanded development of ixazomib for the treatment of patients with advanced malignancy. This study will be conducted in compliance with the protocol, good clinical practice (GCP), applicable regulatory requirements, and International Conference on Harmonisation (ICH).

2. STUDY OBJECTIVES

2.1. Primary Objectives

To evaluate the effect of Ixazomib (MLN 9708) on inducing osteoblast activation as measured by change in serum osteocalcin from baseline to end of study in patients with relapsed/refractory multiple myeloma.

2.2. Secondary Objectives

To evaluate the effect of ixazomib on osteoblast activation as measured by change in radiological studies and bone marrow parameters from baseline to end of study.

To evaluate change from baseline in osteocalcin and other serum bone markers throughout ixazomib treatment.

To evaluate the association between osteoblastic activation and myeloma response to Ixazomib.

To identify predictive factors for Ixazomib-associated osteoblastic activation.

3. STUDY ENDPOINTS

3.1. Primary Endpoint

The primary endpoint of this study is change in serum osteocalcin from baseline to study exit.

3.2. Secondary Endpoint

The secondary endpoints of this study include change in serum osteocalcin and other serum bone markers (BALP, NTX, Vitamin D25) at each study visit, including the exit visit; change in bone marrow parameters (immunohistochemistry, cytogenetics, and flow cytometry) and Dexascan T scores from baseline to end of study; and association between bone marker and radiological changes and anti-myeloma activity in response to Ixazomib therapy.

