		Four patients showed at least a 10% increase in L1–L4 bone mineral density (median: 16%), all of whom responded to therapy (3 = PR, 1 = CR)
Terpos et al.	Post ASCTVDT: $n = 42$ (block $1n = 32$; block 2n = 16)	Only one skeletal-related AE was observed
Ozaki et al.	Bortezomib + dexamethasone: n = 14	In two patients, a "dramatic improvement" in osteolytic lesions was observed (as assessed via multidetector CT scans)

AE, adverse event; ASCT, autologous stem-cell transplant; CR, complete response; CT, computed tomography; MP, melphalan-prednisone; PR, partial response; PTH, parathyroid hormone; VDT, bortezomib-dexamethasone-thalidomide; VISTA, Velcade as Initial Standard Therapy in Multiple Myeloma: Assessment with Melphalan and Prednisone; VMP, bortezomib-melphalan-prednisone.

Multiple studies of bortezomib in both treated and untreated myeloma patients have shown a positive effect of bortezomib on bone health, including fewer bone disease-related MM progression events, increases in bone volume, and improvements in osteolytic lesions. Alkaline phosphatase (total and bone isoenzyme), a marker of bone formation, is increased during bortezomib treatment; the degree of increase may be associated with treatment response. Bortezomib is also related to a reduction in Dickkopf-1, an inhibitor of osteoblast function. Increases of other bone-formation markers and decreases of bone-resorption markers, have also been seen. These clinical effects are supported by preclinical data suggesting bortezomib is associated with an increase in bone formation and osteoblast numbers/activity, arising from direct effects of bortezomib and proteasome inhibition. Thus, evidence indicates that bortezomib exerts a positive effect on bone metabolism in MM and has a bone anabolic effect (16).

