4. STUDY DESIGN

4.1. Overview of Study Design

This is a phase 2 study designed to examine the bone anabolic effect of the next generation proteasome inhibitor, ixazomib, in relapsed/refractory myeloma patients. Treatment consists of ixazomib 4 mg on days 1, 8, 15, 22 of a 28-day cycle, for a maximum of 6 cycles).

General eligibility criteria may be assessed prior to the formal Screening period if it is part of standard clinical practice. However, per the Schedule of Events, formal screening will occur during the Screening period, which may last for up to 35 days prior to initiating study treatment. Determination of relapsed/refractory disease as an entry criterion may be based on patient data obtained during or following the patient's most recent prior antineoplastic therapy.

Study drug (ixazomib 4.0 mg) will be given on Days 1, 8, 15, 22 of a 28- day cycle for a maximum of 6 cycles. Dose modifications may be made based on toxicities during treatment. Patients will be discontinued from the study for progressive disease or unacceptable toxicity.

Treatment periods will be defined as 28-day cycles. Patients will be seen once per treatment cycle (Day 1) during their participation in the active treatment of the study. More frequent follow-up would be only as clinically indicated at the discretion of the treating physician.

Patients will be assessed for disease response and progression. Response will be assessed according to the International Myeloma Working Group (IMWG) criteria (see APPENDIX A) for all patients every 4 weeks for a maximum of 6 cycles (unless disease progression or unacceptable toxicity).

ECOG performance score (APPENDIX B), adverse events (AEs), laboratory values, and vital sign measurements will be collected and assessed throughout the study. Toxicity will be evaluated according to National Cancer Institute Common Terminology Criteria for Adverse Events (NCI CTCAE), version 4.03, effective date 14 June 2010.

Patients will attend an End of Treatment (EOT) visit after completion of their 6 cycles (or at study discontinuation due to progressive disease, unacceptable toxicity, or other reason) and will continue to be followed for survival.

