9. STATISTICAL AND QUANTITATIVE ANALYSES

9.1. Statistical methods

This is a single-arm, phase 2 study to evaluate bone remodeling during ixazomib treatment in relapsed/refractory MM patients. The primary objective is to evaluate the effect of ixazomib on inducing osteoblast activation as measured by change in osteocalcin from baseline to end of study. Ixazomib will be administered orally at the dosage of 4.0 mg weekly in a 28-day cycle for 6 cycles.

The study parameters of interest are described in Section 3. A similar study outlined in Zangari (16) by Terpos (30) evaluated bone markers after treatment with bortezomib in relapsed myeloma and found marked improvement. Terpos (30) reported the median and range osteocalcin level for myeloma patients at baseline and after 8 cycles of treatment with bortezomib. Based on an observed median osteocalcin level (and estimated standard deviation) of 7.46 ng/ml (sd = 12.65) in baseline myeloma patients compared to 19 ng/ml (sd = 18.6) after treatment with bortezomib, differences in pre- and post-

ixazomib continuous study parameters will be evaluated using a nonparametric Wilcoxon sign-rank test for paired data. The correlation between the pre and post treatment groups is assumed to be 0.5. Using the asymptotic relative efficiency method to define power of a nonparametric test relative to a one sample t test, and a significance level of 0.05, the design gives a power of 88% for 20 patients. If normality assumptions are met, then the paired t-test will be used. Difference in binary study parameters will be evaluated using McNemar's test for correlated proportions. Correlation between bone marker parameters will be evaluated using the Spearman correlation coefficient. One-sided pvalues <0.05 will be regarded as statistically significant.

The association between osteoblastic activation and myeloma response to ixazomib and to identify predictive factors for ixazomib-associated osteoblastic activation will be explored using differential expression analysis. All subjects meeting the eligibility criteria who have signed a consent form and have begun treatment will be evaluable for response, toxicities, and safety. Baseline and end of study descriptive statistics will be collected and analyzed per the statistical plan.

10.ADVERSE EVENTS

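### Section 9.1 leaves 23 serial marker comparisons to an unadjusted one-sided 5% rule and a paired test, with no safeguard if patient loss during treatment is related to marker change

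*Combined protocol and SAP*

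**What the plan says.** - **Endpoint.** Section 3.1 names one primary endpoint, the osteocalcin change from baseline to exit. Section 3.2 adds "change in serum osteocalcin and other serum bone markers (BALP, NTX, Vitamin D25) at each study visit, including the exit visit". Section 2.2 makes the course of these markers during treatment an objective.
- **Sampling.** Section 6.2 schedules the four markers at baseline, on Day 1 of Cycles 2 to 6 and at end of study, which is six post-baseline samples.
- **Method.** For continuous parameters, Section 9.1 gives a Wilcoxon signed-rank test on paired data, or a paired t-test if normality holds. Its decision rule is not limited to the primary endpoint: "One-sided pvalues <0.05 will be regarded as statistically significant". It gives no hierarchy, multiplicity adjustment, repeated-measures model, missing-data rule or analysis set for the markers.
- **Who leaves.** Section 4.1: "Patients will be discontinued from the study for progressive disease or unacceptable toxicity". Sections 4.1 and 8.2.6 ask for End of Treatment procedures in patients who stop early, and the Section 7 schedule includes all four markers at that visit.
- **Link to response.** On alkaline phosphatase under bortezomib, Section 1.1.3 says that "the degree of increase may be associated with treatment response". Table 1 there reports a PTH change in responders and no significant change in non-responders.

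**The concern.** Two separate problems follow from having only a pre/post test for a seven-point series.

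First, the significance rule covers every comparison. With four markers at six visits, a small p-value somewhere is far more probable than 5% even if ixazomib does nothing to bone.

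Second, a paired test at an on-treatment visit can use only patients who have that sample. Patients who stop for progression or toxicity are missing from later cycles. If they tend to have smaller marker changes, those who remain are a favourable selection and the later means are too high.

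The study has one arm and 20 patients, so no control group would expose a spurious trend. A rising time course or an isolated significant marker could be read as corroborating the primary result.

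**Working it through.** **1. The plan's own figure, and the SD of change.** Section 9.1 uses "7.46 ng/ml (sd = 12.65) in baseline myeloma patients compared to 19 ng/ml (sd = 18.6) after treatment with bortezomib" and adds: "The correlation between the pre and post treatment groups is assumed to be 0.5".
- Difference: 19 - 7.46 = 11.54 ng/mL.
- SD of change: sqrt(12.65^2 + 18.6^2 - 2 x 0.5 x 12.65 x 18.6) = sqrt(270.69) = 16.45.
- Standardised effect: 11.54 / 16.45 = 0.70.
- The plan states that "the design gives a power of 88% for 20 patients", obtained by an asymptotic relative efficiency (ARE) whose value is not given. A noncentral t calculation, one-sided 0.05, with effective n = 20 x 0.864 (the minimum ARE) gives 87.4%, close to 88%. Other choices give other values (one-sided with ARE 3/pi, 90.4%; two-sided with ARE 0.864, 78.2%), so the match is plausible but not proven. Only the SD of 16.45 is carried forward.

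**2. Number of comparisons.** 4 markers x 6 post-baseline visits = 24, less the primary = 23. Of these, 4 x 5 = 20 are at on-treatment visits and 3 are at exit. If the Cycle 1 sample in the Section 7 table is counted separately from baseline, the total is 4 x 7 - 1 = 27. DXA, marrow and association analyses are not counted.

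**3. False positives if nothing changes.**
- Expected number: 23 x 0.05 = 1.15, whatever the correlation.
- At least one, if independent: 1 - 0.95^23 = 69.3%.
- Independence is unrealistic because all changes in a marker share one baseline. The check simulated exact one-sided signed-rank tests in 20 patients, with assumed visit correlation 0.5-0.9 (constant or decaying) and assumed between-marker correlation 0-0.8:

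| Visit correlation | Marker correlation | Chance of at least one |
|---|---|---|
| 0.5, constant | 0 | 56% |
| 0.5, constant | 0.3 | 50% |
| 0.5, constant | 0.8 | 35% |
| 0.8, decaying | 0.5 | 38% |
| 0.9, decaying | 0.8 | 29% |

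The range is about 30-55%. Random loss of 10% per cycle left the second row at 50%.

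**4. Selective loss at on-treatment visits.** The documents give no dropout rate and no strength for the link, so both are assumptions. The SD of 16.45 is split into true change (13.4) and noise (9.5): sqrt(13.4^2 + 9.5^2) = 16.4. Average true change is set to zero. If staying on drug has correlation r with true change and a share p remains, the mean change among those left is r x 13.4 x phi(z_p)/p, where z_p is the normal quantile of p and phi the normal density.

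| Remaining | phi(z_p)/p | Formula, r = 0.3 to 0.5 | Simulated, 20 patients | One-sided rejection |
|---|---|---|---|---|
| 90% | 0.195 | 0.8 to 1.3 | 0.8-1.2 ng/mL | 8-9% |
| 80% | 0.350 | 1.4 to 2.3 | 1.4-2.3 ng/mL | 10-13% |
| 60% | 0.644 | 2.6 to 4.3 | 2.5-4.2 ng/mL | 12-20% |

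The nominal rejection rate is 5%. With r = 0 the bias is zero.

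A cross-check needs no latent model: overstatement = share lost x difference in mean change between those who stay and those lost. With 10-50% lost and an assumed difference of 5.77 (half of 11.54) to 11.54 ng/mL, it runs from 0.1 x 5.77 = 0.6 to 0.5 x 11.54 = 5.8 ng/mL.

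**5. Does a model on all visits help?** In a simulation with staggered dropout, a random-intercept model cut the bias at the last on-treatment visit from about 2.8-4.2 to 0.8-1.0 ng/mL. It reduces the bias but does not remove it.

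**The case against.** - **Visit-by-visit testing is not written down.** Section 9.1 speaks of pre- and post-treatment differences, and Section 3.2 lists endpoints, not 23 hypothesis tests. This stands: the count is an inference. It is the natural one, because no other method is offered for an endpoint defined at each visit.
- **Early stoppers are sampled at exit.** This stands. The three secondary exit comparisons, like the primary, are meant to include them, so the selection argument concerns Cycles 2 to 6, mainly the later ones.
- **Upward drift is not established.** A reader might infer that later visits will show a rise through attrition alone. The documents do not support that. Section 1.1.3 says only that an association may exist, for alkaline phosphatase under a different drug. Loss through toxicity need not act in the same direction.
- **A chance finding is not clearly likely.** A reader might take the 69% as the answer. It needs independence, which a shared baseline rules out. The correlated range lies mostly below one half, though still about six or more times 5%.
- **Direction differs by marker.** NTX is a resorption marker and vitamin D 25 is not a formation marker, so a chance rise in either would not obviously suggest bone formation. This stands, and it shows a further gap: Section 9.1 fixes a one-sided rule without giving a direction for them.
- **These are secondary endpoints in a small phase 2 study.** True, and the error rate of the primary test is untouched. But the significance rule as written applies to the secondary results too.

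**Conclusion.** The concern holds in a limited form. Read together, Sections 3.2, 6.2 and 9.1 lead to 23 unadjusted one-sided comparisons besides the primary. With no true change, 1.15 would be falsely significant on average, and the chance of at least one is about 30-55% under the assumed correlations.

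Mean change at on-treatment visits may also be overstated, by roughly 1 to 4 ng/mL of osteocalcin over 90% to 60% remaining. That rests on an assumed correlation of 0.3-0.5 between true change and staying on drug. The documents fix neither that link nor the dropout rate, and without the link there is no bias. The finding is a risk that the plan leaves unhandled. It does not predict a false trend and does not challenge the primary test.

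**What to change.** In Section 9.1:
1. Limit the significance statement to the primary osteocalcin test.
2. Analyse each serial marker with one mixed model on all visits: log scale, visit as a factor, baseline as covariate, patient as random effect, and one contrast per marker named in advance.
3. Report secondary results as estimates with confidence intervals, and show the number of patients at each visit.

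This needs no new patients, samples or visits. It costs a little more programming, and fewer results can be called significant. The model still relies on the observed values explaining the loss, so some bias can remain.

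A Bonferroni correction is a poorer choice. At 0.05/23 = 0.0022, the power of one test at the plan's osteocalcin effect (ARE 0.864) would fall from 87% to 38%.
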